#### **7.2.4 ECG evaluations**

Heart rate, PR, QRS, QT, QTcF, and RR intervals will be obtained from ECGs (12-lead or 5-lead) for each participant during the study. ECG data will be read and interpreted locally.

Categorical analysis of QT/QTcF interval data based on the number of participants meeting or exceeding predefined limits in terms of absolute QT/QTcF intervals or changes from baseline will be presented.

Summary statistics will be provided by treatment group and visit/time.

#### **7.2.5 Clinical laboratory evaluations**

Summary statistics will be provided by treatment group and visit/time.

In case for one parameter multiple types of assessments were reported for the same visit/assessment the following rules are applied for any analysis e.g. summarizing the results:

- In case both absolute counts and percentages (e.g. “bands” or ratios) are provided, absolute counts are used.
- In case both Urea and BUN parameters are provided, Urea is used.

## Commercially Confidential Information

**7.2.6 Adverse events**

All information obtained on adverse events will be listed by treatment and subject.

Summary tables for adverse events (AEs) will summarize only on-treatment events, with a start date during the on-treatment period (treatment-emergent AEs).

The number and percentage of subjects with adverse events will be tabulated by body system and preferred term with a breakdown by treatment. Separate summaries will be provided for study medication related adverse events and other significant adverse events leading to discontinuation.

The number of deaths resulting from SAEs suspected to be related to study treatment and SAEs irrespective of study treatment relationship will be provided by SOC and PT.

A subject with multiple adverse events within a body system is only counted once towards the total of this body system and treatment.

For the legal requirements of ClinicalTrials.gov and EudraCT, two tables are required: on treatment emergent adverse events which are not serious adverse events and on treatment emergent serious adverse events and SAE suspected to be related to study treatment will be provided by system organ class and preferred term on the safety analysis set.

If for a same patient, several consecutive AEs (irrespective of study treatment causality, seriousness and severity) occurred with the same SOC and PT:

- a single occurrence will be counted if there is  $\leq 1$  day gap between the end date of the preceding AE and the start date of the consecutive AE
- more than one occurrence will be counted if there is  $> 1$  day gap between the end date of the preceding AE and the start date of the consecutive AE.

For occurrence, the presence of at least one SAE / SAE suspected to be related to study treatment / non SAE has to be checked in a block e.g., among AE's in a  $\leq 1$  day gap block, if at least one SAE is occurring, then one occurrence is calculated for that SAE.

**7.2.7 Graphical presentation**

For all vital signs, ECGs and laboratory parameters the following graphical presentations will be provided:

Panels of individual spaghetti plots over time for each parameter and their change from baseline will be drawn. The profiles of all participants in the respective treatment group will be included in these graphs as grey lines in the background and the respective individual participants profile will be plotted with darker color in the foreground. The respective applicable normal ranges will be added and it will be indicated by a symbol if a patient died.

Means (+/- SE) will be plotted over time by treatment group.

Commercially Confidential Information

---

Commercially Confidential Information

## 10 Appendix

### 10.1 Units and conversions

Special care must be taken with respect to converting lab parameters prior to applying the scoring described below to avoid propagation of rounding errors. The following principles will be applied:

- If the unit of the original lab assessment from the local lab is equal to the unit used in the scoring table, this original value is used.
- In case the SI unit which is available within the SDTM data sets is equal to the unit used in the scoring table, the value converted to SI units is used.
- If neither the original nor the SI unit are matching the unit used in the scoring table then convert the original value from the local lab to the unit required by the scoring table. Note that for some parameters there are scoring tables available for different units.
- Do not convert the value in SI units further.
- Do not apply rounding to the precision required in the scoring table only after conversion to the unit used in the scoring table has been done.

#### 10.1.1 Conversion for absolute differential blood counts

If not reported, the absolute differential blood counts can be derived if

- % of blood count (on 0-1 scale) (e.g. for Neutrophils, Eosinophils, Lymphocytes, Monocytes, Basophils)
- Total WBC

is available via the following formula:

$$\text{absolute differential blood count} = \text{total WBC} * \% \text{ of blood count.}$$

## 10.2 APACHE II

The APACHE II score is derived from a number of different clinical endpoints according to the scoring table as outlined in ([Knaus et al., 1985]):

### 1. Body temperature (°C)

Depending on the collection method selected apply the following correction factors before scoring:

- Core: no correction needed
- Axillary: + 1.0 °C
- Oral: + 0.5 °C
- No method selected: no correction.

### 2. Mean Arterial Pressure (mmHg)

In case the “method” is reported as “calculated” confirm the calculation by applying the following formula:  $MAP = [SBP + (2x DBP)] / 3$ . If the reported and recalculated numbers differ by more than 10% use the recalculated value (i.e. if reported value < 0.9\* recalculated value or reported value > 1.1\* recalculated value)

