#### 6.1.1 Variable

The primary clinical question of interest is: What is the effect of DFV890 in addition to SoC versus SoC alone in SARS-CoV-2 infected patients with COVID-19 pneumonia and impaired respiratory function on APACHE II severity of disease score taking into account early discharge from hospital or death but regardless of investigational treatment discontinuation?

The justification for the primary estimand is that it will capture the combined effect of investigational treatment in participants who remain in hospital for 14 days, the effect on early discharge within 14 days and the effect on death rate within 14 days, in a manner than reflects clinical practice. In this document the primary estimand will be referred to as the “**combined APACHE II score**”.

The primary estimand is described by the following attributes:

- **Population:** SARS-CoV-2 infected patients with COVID-19 pneumonia and impaired respiratory function. Further details about the population are provided in the protocol (Section 5)
- **Endpoint:** APACHE II severity of disease score on Day 15 or on day of discharge (whichever is earlier) with worst case imputation for death. Participants who die on Day 15 or earlier will be assigned the highest observed APACHE II score of any of the participants at any time during the trial. Note this imputation for death takes precedence over the APACHE II score on day of discharge.
- **Treatment of interest:** the randomized treatment (the investigational treatment DFV890 in addition to SoC or control treatment of SoC alone).
- **Handling of remaining intercurrent events:** Treatment discontinuation for any reason will be ignored and thus follow a treatment policy strategy i.e. participants who discontinue treatment will be treated in the same manner as those that continue the treatment as planned.
- **Summary measure:** The difference in variable means between treatments.

APACHE II scores are on a range between 0 and 71 points, however, in practice it is rare for any patient to accumulate more than 55 points. A decrease in the APACHE II score is considered a favorable outcome.

The APACHE II scores are derived from a number of different clinical endpoints according to the scoring table as outlined in (Knaus et al., 1985) and listed in the [Appendix](#). The handling of missing data is described in [Section 6.1.6](#).

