### 6.1.3 Statistical model, assumptions and hypotheses

The combined APACHE II endpoint as described in the estimand above is assumed to follow a normal distribution.

The primary endpoint will be analyzed by an analysis of covariance model including treatment group and the three stratification factors as factors and baseline APACHE II score as a covariate. The analysis will be performed on the safety analysis set. The mean differences of DFV890 in addition to SoC vs SoC alone will be reported with 90% confidence intervals (CIs). The 1-sided p-value for the overall treatment factor will be reported.

The primary objective will be achieved if the null hypothesis that DFV890 in addition to SoC is not different to SoC alone is rejected using a one side alpha of 10%.

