### SDTM Mapping strategy

APACHE II specific mapping strategy: It provides guidance on how the result variables (RSORRES, RSSTRESC, and RSSTRESN) should be populated for the measure. All original results are represented with preferred terminology in RSORRES. This result is then transformed into a standard numeric score in RSSTRESN and a character representation of the standard numeric score in RSSTRESC.

To obtain the total APACHE II score all 14 derived values of RSSTRESN are then added up. If one item is missing the APACHE II score at STDM level for this visit is missing. Missing data imputation will be implemented at ADAM level.

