#### 10.2.1 APACHE II Scoring

Temperature (°C)

RSORRES	RSSTRESC	RSSTRESN
>=41	4	4
39-40.9	3	3
38.5-38.9	1	1
36-38.4	0	0
34-35.9	1	1
32-33.9	2	2
30-31.9	3	3
≤29.9	4	4

Mean Arterial Pressure (mmHg)

RSORRES	RSSTRESC	RSSTRESN
>=160	4	4
130-159	3	3
110-129	2	2
70-109	0	0
50-69	2	2
≤49	4	4

Heart rate (beats/min)

Does the participant have a pacemaker?	RSORRES	RSSTRESC	RSSTRESN
Irrespective	$\geq 180$	4	4
Irrespective	140-179	3	3
Irrespective	110-139	2	2
No/unknown	70-109	0	0
No/unknown	55-69	2	2
No/unknown	40-54	3	3
No/unknown	$\leq 39$	4	4
Yes	$\leq 109$	0	0

Respiratory rate (BREATHS/MIN)

Note: Ventilated or non-ventilated patient scores will be the same as per table below

RSORRES	RSSTRESC	RSSTRESN
$\geq 50$	4	4
35-49	3	3
25-34	1	1
12-24	0	0
10-11	1	1
6-9	2	2
$\leq 5$	4	4

Oxygenation:

- If  $FiO_2 \geq 0.5$  the use A-aDO2 (mmHg)

RSORRES	RSSTRESC	RSSTRESN
$\geq 500$	4	4
350-499	3	3
200-349	2	2
$< 200$	0	0

- If  $FiO_2 < 0.5$  then use PaO2 (mmHg)

RSORRES	RSSTRESC	RSSTRESN
$> 70$	0	0
61-70	1	1
55-60	3	3
$< 55$	4	4

Arterial pH

- Use arterial pH if reported

RSORRES	RSSTRESC	RSSTRESN
$\geq 7.7$	4	4
7.6-7.69	3	3
7.5-7.59	1	1
7.33-7.49	0	0

7.25-7.32	2	2
7.15-7.24	3	3
<7.15	4	4

- Alternatively use Serum HCO3 (mmol/L)

RSORRES	RSSTRESC	RSSTRESN
>=52	4	4
41-51.9	3	3
32-40.9	1	1
22-31.9	0	0
18-21.9	2	2
15-17.9	3	3
<15	4	4

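### A mean arterial pressure marked as calculated is kept when it is up to 10% away from the value recalculated from SBP and DBP, which leaves small but avoidable noise in the APACHE II score

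*SAP*

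**What the plan says.** SAP Section 10.2, item 2, covers MAP readings whose method is given as calculated: "In case the “method” is reported as “calculated” confirm the calculation by applying the following formula", namely (SBP + 2 × DBP)/3. It continues: "If the reported and recalculated numbers differ by more than 10% use the recalculated value". A bracket after this puts the limits at 0.9 and 1.1 times the recalculated value, which agrees with the 10% wording. By implication, a reported value inside those limits is the one scored. The SAP gives no reason for the tolerance, and no other section overrides it.

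Section 10.2.1 converts MAP to points: 160 or more, 4; 130–159, 3; 110–129, 2; 70–109, 0; 50–69, 2; 49 or less, 4. The SDTM mapping text in Section 10.2 then says: "To obtain the total APACHE II score all 14 derived values of RSSTRESN are then added up". The total is the primary endpoint in Section 6.1.1, "APACHE II severity of disease score on Day 15 or on day of discharge (whichever is earlier) with worst case imputation for death". The model in Section 6.1.3 includes "the three stratification factors as factors and baseline APACHE II score as a covariate", so the MAP rule acts on the covariate as well as the outcome.

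**The concern.** A calculated MAP is not a separate measurement. It is a function of SBP and DBP, so once those two are recorded the reported figure adds no information. A gap beyond rounding means that a different formula was used, that there was an arithmetic slip, or that the figures came from different readings. The plan trusts SBP and DBP enough to overrule the site at 11% but not at 9%, and gives no reason for the difference.

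The tolerance is also wide relative to the scoring bands. A kept discrepancy can carry a reading across a cut-point and change the item by up to 2 points. What is at stake is precision: avoidable error in one component of the primary score, at baseline and at the endpoint visit.

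**Working it through.** **Inputs from the SAP.** The formula and 10% rule (Section 10.2, item 2), the MAP bands (Section 10.2.1), the sum of 14 items (Section 10.2) and the 0–71 range (Section 6.1.1). The 10% is a convention, with no derivation in the SAP to reproduce.

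**1. Width of the tolerance at the cut-points.** 0.10 × 70 = 7 mmHg and 0.10 × 110 = 11 mmHg. Crossing either cut-point is worth 2 points.

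**2. Worked readings.**
- 145/85: (145 + 170)/3 = 105, 0 points. A reported 115 has ratio 115/105 = 1.095. It is kept and scores 2.
- 144/87: (144 + 174)/3 = 106, 0 points. A reported 112 has ratio 1.057. It is kept and scores 2.
- 110/55: (110 + 110)/3 = 73.3, 0 points. A reported 67 has ratio 0.914. It is kept and scores 2.
- 140/90: (140 + 180)/3 = 106.7, 0 points. A reported 118 has ratio 1.106. It is replaced, and the item scores 0.

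**3. Where the rule can matter.** The rule was applied to every whole-number recalculated MAP from 40 to 180 (141 values), crossed with whole-number reported values.

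| Recalculated MAP (mmHg) | Can a kept discrepancy change the score? |
|---|---|
| 46–54, 64–76, 100–143, 146–176 | Yes (9 + 13 + 44 + 31 = 97 values) |
| 40–45, 55–63, 77–99, 144–145, 177–180 | No (6 + 9 + 23 + 2 + 4 = 44 values) |

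The change is 2 points around 50, 70 and 110, and 1 point around 130 and 160.

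**4. Illustration A, on assumed figures.** Recalculated MAP is taken as normal with mean 80–95 and SD 12–15, and kept errors as uniform. None of this is in the SAP.

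| Largest kept error | Discrepant readings that change score |
|---|---|
| ±2% | about 2–3% |
| ±5% | about 4–6% |
| ±10% | about 8–13% |

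The mean shift is at most about 0.06 points per discrepant reading.

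**5. Illustration B, on assumed figures.** Suppose a site used the simple average (SBP + DBP)/2. The excess over the correct value is (SBP + DBP)/2 − (SBP + 2 × DBP)/3 = (SBP − DBP)/6. The value is kept when this is at most 0.1 × (SBP + 2 × DBP)/3. Multiplying by 30 gives 5(SBP − DBP) ≤ SBP + 2 × DBP, that is, SBP ≤ 1.75 × DBP. For 145/85 the ratio is 1.71, so it is kept.

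Simulated shares, with SD 16 for SBP and 10 for DBP:

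| Mean BP | SBP–DBP correlation | Pass the check | Mis-scored, of all readings |
|---|---|---|---|
| 120/72 | 0 | 60% | 4% |
| 120/72 | 0.7 | 68% | 9% |
| 130/78 | 0 | 61% | 12% |
| 130/78 | 0.7 | 69% | 17% |

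This error runs mostly upwards, adding on average about 0.06 to 0.31 points per reading at such a site. Nothing in the SAP indicates that any site calculates MAP in this way.

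**The case against.** The best defence is that a tolerance respects source data. The SAP does not say that the SBP and DBP used for the check belong to the same reading as the reported MAP. A small gap may be rounding, a second reading, or a typing error in SBP or DBP; in the last case the recalculated value is the wrong one. The rule is also fully specified, consistent with itself and the same for both arms. The caution in Section 10.1 about propagating rounding errors concerns laboratory parameters, so it is not breached.

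Most of this stands, and it limits what may be claimed. A reader might infer that the plan knowingly scores miscalculated values while holding the exact one. The document does not support that, because a gap under 10% is not proof of an error and the recalculated figure is only as good as the recorded pressures. A reader might also infer site-specific error or a biased treatment comparison. Nothing in the SAP shows either: the rule does not refer to treatment, and the simple-average site is hypothetical.

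The defence does not justify the tolerance itself. Doubt about the recorded SBP and DBP applies above 10% as well, where the plan relies on them without reserve. The pairing problem is met by requiring that both come from the same assessment.

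**Conclusion.** The point holds as a minor, inexpensive improvement. The rule keeps a reported calculated MAP within 10% of the recomputed value, and under the SAP's own bands this can shift the item by up to 2 points in the primary score and in its baseline covariate. That part needs no outside assumption.

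The likely effect is small. It touches one of 14 items, at most 2 points on a scale described by "APACHE II scores are on a range between 0 and 71 points". It arises only for readings marked as calculated, only when there is a discrepancy, and only when a cut-point is crossed. For whole-number values it cannot arise at a recalculated MAP of 77–99. The expected result is slight noise that does not depend on arm.

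The SAP does not give the frequency of discrepancies, so no effect on the treatment difference or on power can be computed, and none is claimed. The percentages in both illustrations rest on assumed blood pressure distributions and assumed errors. They indicate scale and are not estimates for this trial.

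**What to change.** In SAP Section 10.2, item 2, replace the 10% rule with: *If the method is calculated and SBP and DBP from the same assessment are available, use the recalculated value; use the reported value only if SBP or DBP is missing.* MAP readings with any other method are unaffected.

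The cost is one sentence. The recalculation is already required for the comparison, and no new data are needed. The item then becomes reproducible from the recorded pressures. The 10% comparison can be kept as a data-query trigger if the team finds it useful, but that is a data management matter and need not be in the SAP.

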### 3. Heart Rate (beats per minute)

If the participant has a pacemaker any HR <= 109 bpm will be scored to 0.

### 4. Respiratory Rate (breaths per minute)

### 5. Oxygenation: depending on the Fraction of inspired Oxygen (FiO2, where FiO2 is a value between 0 and 1 (i.e. not on % scale)):

- If FiO2 < 0.5: use PaO2 (mmHg)
- If FiO2 >= 0.5: use A-aDO2 (mmHg): where A-aDO2 is calculated as  $A-aDO2 = (FiO2 \times 713 - PaCO2/0.8) - PaO2$

In case PaO2 is not available for a certain visit it can be derived from SPO2 if available instead using the following conversion table:

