### 6.1.6 Missing data

Missing data for the APACHE II score will be handled as follows:

- Missing values for age at screening will be replaced by using the stratification information assigning 3 points to participants up to 65 years ( $\leq 65$  years) and 5 points to participants above 65 years.
- Missing information on acute renal failure status: use Serum Creatinine values without renal status information.
- Subscores of the Glasgow Coma Score (i.e. responses to Best Eye Response, Motor Response, Verbal Response) scored as “untestable”, “unknown” or missing will be replaced by the last available actual score. The response “untestable” is selected if the patient is unconscious (e.g. through sedation in case of mechanical ventilation).
- Missing values in any of the other parameters required for the derivation of the APACHE II score will be replaced by the last available assessment, as long as data is not carried forward by more than 4 days.

For a given visit, these missing data rules will only be applied if for at least one of the parameters contributing to the APACHE II score a value was reported for this specific visit.

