#### **7.2.3 Vital signs**

Vital sign measurements include respiratory rate, pulse rate (PR), systolic and diastolic blood pressure, mean arterial pressure body temperature, weight and BMI. Peripheral oxygen saturation on room air or on supplemental oxygen is also measured at the same time as the vitals. In case oxygen saturation is reported for both room air and under supplemental oxygen, the value for room air is included in summary presentations and analysis. For participants requiring supplemental oxygen, the oxygen flow rate (L/min) and/or FiO2 is also recorded.

Summary statistics will be provided by treatment group and visit/time.

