**Table 10-1 Conversion of SpO2 to PaO2**

SpO2 (%)	PaO2 (mmHg)
80	44
81	45
82	46
83	47
84	49
85	50
86	52
87	53
88	55
89	57
90	60
91	62
92	65
93	69
94	73
95	79
96	86
97	96
98	112
99	145

6. Arterial pH: if Arterial pH is not available use Serum HCO3 (venous mmol/L) instead
7. Serum Sodium (mmol/L)
8. Serum Potassium (mmol/L)
9. Serum Creatinine (mg/dL=mg/100mL)
10. Hematocrit (%)
11. White Blood Count ( $10^9/L = 1000/mm^3 = 10^3/mm^3$ )
12. Age at Screening (years)
13. Chronic Health Points at Screening:  
Points are assigned only if for this patient “Did the subject experience Severe organ system insufficiency or is immunocompromised ?” is selected as “yes”.
  - If “Did the subject experience Severe organ system insufficiency or is immunocompromised ?” = “no”, no points are assigned and a record should not be created for this question in the SDTM data set.
  - If “Did the subject experience Severe organ system insufficiency or is immunocompromised ?” is selected as “yes” Chronic Health points will be derived from “Admission Classification”:
    - Medical(non-operative)
    - Emergency post-operative
    - Elective post-operative

If in this scenario none of these conditions is selected the Chronic Health points will be set to 0.

14. Glasgow Coma Score: First each sub-score is scored according to the scoring table below

- Best Eye Response
- Motor Response
- Verbal Response

Then these three subscores are added up to obtain the scoring of the “Total Glasgow Coma Score”. The value included in the APACHE II for Glasgow-Coma-Score is then = 15 – “Total Glasgow Coma Score”.

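### At FiO2 of 0.5 or more the APACHE II oxygenation item needs PaCO2, whose only fallback is a 4-day carry-forward; when that fails, a living participant on high oxygen has no primary score

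*SAP*

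**What the plan says.** Section 10.2, item 5, splits the oxygenation item by FiO2. Below 0.5 it is scored from PaO2 alone. Otherwise the rule is "If FiO2 >= 0.5: use A-aDO2 (mmHg): where A-aDO2 is calculated as" (FiO2 × 713 − PaCO2/0.8) − PaO2. PaCO2 therefore enters the total score only in the high-oxygen branch.

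Two other inputs have a same-visit substitute:
- PaO2: "In case PaO2 is not available for a certain visit it can be derived from SPO2 if available", through Table 10-1.
- Arterial pH: "if Arterial pH is not available use Serum" bicarbonate from a venous sample.

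No such substitute is given for PaCO2. The SDTM mapping text in Section 10.2 says "If one item is missing the APACHE II score at STDM level for this visit is missing", and adds "Missing data imputation will be implemented at ADAM level". In Section 6.1.6 the rule that reaches PaCO2 is the general one for parameters not named separately: a missing value "will be replaced by the last available assessment, as long as data is not carried forward by more than 4 days". Section 4.2 lets unscheduled values feed that carry-forward. Section 6.1.8 takes the Day 15 score, or the discharge-visit score if discharge is earlier, and gives deaths by Day 15 the worst score seen in the trial. Section 6.1.3 analyses the result by ANCOVA on the safety set.

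**The concern.** By giving substitutes for PaO2 and pH, the plan allows for visits without an arterial sample. In the high-oxygen branch those substitutes do not suffice: PaO2 can be read from SpO2, but the gradient still cannot be computed without PaCO2. If carry-forward also fails, one absent input removes a 14-item score.

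The gap opens only at FiO2 0.5 or above, so any loss is tied to severity. The people exposed are alive, still need much oxygen at the scoring visit, and would be expected to score high. The visible text does not say how they enter the primary comparison. A plausible route is escalation from below FiO2 0.5 shortly before the scoring visit, because PaCO2 was not needed for the score before that.

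**Working it through.** The SAP states no rate of missing scores, so there is no figure to reproduce. The check applies its own formula, score bands and conversion table.

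**1. Same data, two branches.** Take SpO2 92% (PaO2 65 mmHg by Table 10-1), a venous bicarbonate, all other items present, and no PaCO2 at the visit or in the previous 4 days.
- FiO2 0.4: PaO2 65 lies in the 61–70 band, 1 point. The total is complete.
- FiO2 0.6: the gradient is 0.6 × 713 − PaCO2/0.8 − 65 = 362.8 − PaCO2/0.8. It cannot be computed, so the item and the total are missing.

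**2. Reach of the carry-forward.** Hospital assessments are every 2 days (Section 1.4), so a 4-day window spans about two earlier scheduled visits plus any unscheduled sample. It closes the gap only if a PaCO2 was obtained in that time. The visible text has no further rule.

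**3. How much PaCO2 matters to the item.** Bands: 500 or more, 4 points; 350–499, 3; 200–349, 2; below 200, 0. PaCO2 is varied over an assumed 25 to 60 mmHg, which moves the gradient by 35/0.8 = 43.75 mmHg; the closed bands are about 150 mmHg wide.

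| FiO2 | SpO2 (PaO2) | Gradient at PaCO2 25 | at 40 | at 60 | Points |
|---|---|---|---|---|---|
| 0.5 | 96% (86) | 239.2 | 220.5 | 195.5 | 2, 2, 0 |
| 0.6 | 92% (65) | 331.6 | 312.8 | 287.8 | 2, 2, 2 |
| 0.8 | 92% (65) | 474.1 | 455.4 | 430.4 | 3, 3, 3 |
| 1.0 | 92% (65) | 616.8 | 598.0 | 573.0 | 4, 4, 4 |

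Over FiO2 0.50 to 1.00 in steps of 0.05 and SpO2 80% to 99% (11 × 20 = 220 cells), the points are the same for every PaCO2 from 25 to 60 in 168 cells (76%). A fixed 40 mmHg is off by at most 1 point in 48 cells and at most 2 points in 4. The cells are unweighted and are not proportions of patients.

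**4. Error of a fixed 40 mmHg.** Simulation with FiO2 uniform 0.5–1.0, PaO2 uniform 55–110 mmHg and PaCO2 normal (all assumed). Error is the imputed minus the true item score.

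| PaCO2 mean (SD) | Items changing category | Mean error, points |
|---|---|---|
| 38 (7) | 4.2% | −0.01 |
| 35 (7) | 4.9% | −0.04 |
| 45 (10) | 6.9% | +0.05 |
| 45 (12) | 8.0% | +0.05 |
| 50 (15) | 11.7% | +0.10 |

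**5. What losing the score could cost.** Suppose a share q of an arm is lost and would have scored D points above the rest, whose mean is m. The full mean is (1 − q)m + q(m + D) = m + qD, so the arm mean is understated by qD. With assumed values, q = 2% and D = 5 give 0.1 point; q = 20% and D = 10 give 2.0 points. The treatment difference is distorted by the difference in qD between arms, and not at all if the arms lose equally.

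**The case against.** The strongest reply is that the plan already has a remedy. Missing at SDTM level is not final, imputation follows, and carry-forward covers PaCO2 and may use unscheduled samples. With visits every 2 days it may fill most gaps. Deaths by Day 15 are scored whatever their oxygenation data, so part of the sickest group is unaffected. Whether a blood gas is required at high FiO2 may be settled in the protocol, which is not at hand, and the supportive analysis in Section 6.1.9 is redacted. All of this stands, and it narrows the exposed group to living participants at FiO2 0.5 or above with no PaCO2 in the window. It does not supply a rule for them; Section 6.1.6, where that rule would belong, contains none.

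Three stronger readings are not supported:
- A reader might infer that PaCO2 has no substitute at all, or that the primary score generally goes missing in the most hypoxic participants. The carry-forward contradicts the first. For the second, the substitutes show that the plan allows for absent blood gases, not how often they are absent.
- A reader might infer a demonstrated bias toward no difference. That direction needs the control arm to lose more, or higher-scoring, participants, which no text shows.
- Section 7.2.3 says that when "oxygen saturation is reported for both room air and under supplemental oxygen, the value for room air is included in summary presentations and analysis". A reader might infer that room-air SpO2 is paired with FiO2 on oxygen in item 5. That rule sits in the safety chapter, and nothing applies it to APACHE II.

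It is also fair that 40 mmHg comes from no document and that its error rate depends on the assumed PaCO2 distribution, hence the range above.

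**Conclusion.** The point holds in a limited form and merits a cheap improvement. Followed as written, the SAP leaves a living participant at FiO2 0.5 or above, with SpO2 but no PaCO2 at the visit or within 4 days, without a total score and without a visible route into the primary ANCOVA, while the same data below FiO2 0.5 are scored. That the loss is linked to oxygen need follows from the rule itself. Its frequency is unknown, and the 0.1 to 2.0 points per arm are illustrations on assumed q and D, not estimates. Losing a 14-item score is out of proportion to the missing input: over the assumed 25 to 60 mmHg, PaCO2 leaves the oxygenation points unchanged in 76% of the unweighted cells and shifts them by at most 2 points from the value at 40 mmHg in the rest.

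**What to change.** Add to Section 10.2, item 5: *If FiO2 is 0.5 or above and no PaCO2 is available at the visit or within the 4-day carry-forward window, A-aDO2 is computed with PaCO2 set to 40 mmHg, for scoring only.* State that 40 mmHg is an assumed normal reference value. Report the number of such cases by arm, and repeat the primary analysis with a low and a high value, for example 25 and 60 mmHg.

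The cost is a few lines in the SAP, the matching derivation code and two reruns of the ANCOVA. The downside is that about 4% to 12% of the items so imputed would fall in another category under the assumed distributions, with a mean error within about 0.1 point.

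Optionally, and separately from this point, item 5 could state that SpO2 and FiO2 must come from the same condition.
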